## **Ultrasound-guided Pectoralis 1 and 2 block with liposomal bupivacaine for breast surgery: A prospective randomized study.**

**Design:** Level I randomized prospective outcomes study comparing two groups of patients. One group will receive liposomal bupivacaine for a pectoralis (“Pec”) block infiltration and the other will receive incisional bupivacaine infiltration by the surgeon.

**Sample Size:** 112 patients

**Study Duration:** Approximately 18 months

**Population:** Patients presenting to the University of Minnesota Medical Center, M health Ambulatory Surgery or Fairview Maple Grove Clinics Ambulatory Surgery Center, for elective lumpectomy and partial mastectomy procedures +/- axillary node dissection.

### **Primary Objective:**

1. To determine if liposomal bupivacaine Pec infiltration provides decreased peri-operative opioid usage when compared to incisional bupivacaine infiltration.

### **Secondary Objectives:**

1. To determine if a pectoralis 1 and 2 block with liposomal bupivacaine provides decreased maximal pain scores when compared to incisional bupivacaine infiltration
2. To determine if a pectoralis 1 and 2 block with liposomal bupivacaine provides decreased rate of conversion to general anesthetic when compared to incisional bupivacaine infiltration
3. To determine if a pectoralis 1 and 2 block with liposomal bupivacaine improves quality of recovery score post-operatively when compared to incisional bupivacaine infiltration.
4. To observe the effect on chronic postoperative pain in patients who have breast surgery.

## **2. Synopsis and Medical Application:**

### **Specific Aims:**

#### **Primary Hypothesis:**

A pectoralis 1 and 2 block with liposomal bupivacaine will result in decreased total opioid usage relative to bupivacaine infiltration after an elective partial mastectomy

**Secondary Hypotheses:** A pectoralis 1 and 2 block with liposomal bupivacaine will result in improved quality of recovery score, decreased maximal pain scores, and decreased rate of conversion to general anesthetic.

## **Background and Significance:**

Liposomal bupivacaine is a multivesicular formulation of bupivacaine that has been shown to provide up to 72 hours of analgesia compared to bupivacaine, which provides up to 24 hours of analgesia post injection. These two medications have been compared in incisional infiltration but have yet to be compared in the setting of a pectoralis (“Pec”) infiltration vs incisional infiltration. A Pec 1 infiltration is an injection of local anesthetic in between the pectoralis major and pectoralis minor muscle layers. A Pec 2 infiltration is an injection of local anesthetic between the pectoralis minor and serratus anterior muscle layers or deep to the serratus anterior. These layers are found using an ultrasound, which is a beam of high frequency sound that allows one to visualize images in the body. With the ultrasound it is possible to visualize the needle as it pierces the fascial covering of the pec minor or serratus anterior layer and watch as the local anesthetic is injected into this plane. This is done on both sides of the chest wall to provide analgesia to the skin, muscle, and facial layers of the chest wall if the procedure is bilateral or just on one side if unilateral. Data has shown the Pec infiltration to provide useful pain control after breast surgery, however it is of limited duration provided by bupivacaine.

Incisional infiltration. The surgeon will infiltrate local anesthetic (bupivacaine) into the surgical site at the start of the procedure, within the subcutaneous and dermal regions immediately surrounding the incision. Additional incisional bupivacaine infiltration will be performed as needed throughout the procedure. Accidental intravascular injection is minimized by continuous needle movement and frequent aspiration.

This will be the first study of its kind looking prospectively at Pectoralis 1 and 2 blocks with liposomal bupivacaine compared to surgeon infiltration for postoperative pain in breast partial mastectomy procedures.

## **Subjects:**

Demographics: All patients undergoing elective breast lumpectomy and partial mastectomy at the University of Minnesota Medical Center, M health Ambulatory Surgery Center or Fairview Maple Grove Clinics Ambulatory Surgery Center, with all Pec infiltration to be placed by the Primary Investigator and other staff anesthesiologists on the perioperative and interventional pain service and surgeon infiltration to be done by the co-investigators.

## **Entry Criteria:**

Subjects will be evaluated and confirmation of the following will be documented:

### **Inclusion criteria assessed during surgery:**

- All patients undergoing partial mastectomy procedures.
- Ages 18-75

**Exclusion criteria:**

- Patient on chronic anticoagulation
- Pregnant women
- Non-english speaking patients
- Any individuals who are unable to give informed consent
- Any individual with diminished capacity to give informed consent
- Allergy to local anesthetics
- Patients who remain intubated overnight after surgery or who are unable to provide information regarding their pain immediately postoperatively
- Daily use of opioid for more than three weeks
- Significant liver disease, defined as liver enzymes greater than 3x the upper limit of normal
- Lack of patient cooperation including those patients who refuse a MAC anesthetic
- Patient with pectoral muscle involvement of tumor
- Contraindication to regional anesthesia
  - Infection at injection site
  - Inability to guarantee sterile equipment or sterile conditions for the block
  - Patient refusal
  - Severe Coagulopathy or bleeding disorder

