**Randomization procedure:**

Patients will be identified by members of the treatment team in either the surgeon's clinic, pre-assessment clinic, or preoperative area. Patients who have opted out of research will not be asked to participate in the study. Patients will be approached to consent for the study by a surgeon, anesthesiologist, or member of the research team. Patients who agree to participate in the study will sign both a study consent and HIPAA authorization allowing the use of specified information contained in medical records for research purposes.

A random number generator will be used to determine if the patient will have pectoralis liposomal bupivacaine infiltration or bupivacaine infiltration directly into the incision space. The primary or co-investigator will access the number generator in the pre-op area. The website [www.random.org](http://www.random.org) will be used as the random number generator.

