**Treatment technique:**

For the Pec infiltration, the patient will be in the supine position. The pectoralis major and pectoralis minor muscle layers will be identified via ultrasound. Using sterile technique, a nerve block needle will be inserted and advanced under ultrasound guidance until it is below the fascial covering of the pec minor muscle layer. Gentle aspiration for air or blood will be performed in 5cc incremental doses. Then injection of 10 mL of bupivacaine 0.25% with epinephrine 1:200,000 and 10mL of a mixture of liposomal bupivacaine and saline (5 mL liposomal bupivacaine and 5 mL saline) for a total injection for pec 1 block of 20 mL. For each 5cc of local anesthetic injected, aspiration will be performed. Upon completion of the injection the needle will be removed. We will then use the ultrasound probe to identify the second rib on anterolateral chest wall and

move the probe to the 4th rib. Here we will identify the pec minor and serratus anterior muscles. We will advance our needle under ultrasound-guidance beneath pec minor and above serratus anterior or if unable to visualize the serratus/pec minor border will inject under the serratus anterior. Here we will inject 10 mL 0.25% bupivacaine with epinephrine 1:200,000 followed by 20 mL mixture of 15 mL liposomal bupivacaine and 5 mL saline for a total volume of 30mL for Pec 2 Block. Upon completion of the injection, the needle will then be removed and the patient will be monitored in the preoperative area until he/she is brought into the operating room for their procedure.

If deemed necessary for coverage the surgeon will be allowed to inject additional local anesthetic up to a maximum of 40 mL of 0.25% bupivacaine. This will be noted in the chart.

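### One exclusion criterion can only be known after randomization and the Pec block, and nothing requires eligibility to be settled before the draw, so patients can be removed for events that treatment may influence.

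*Combined protocol and SAP*

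**What the plan says.** All references are to the combined protocol and SAP.

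- **Allocation.** Randomization procedure: "The primary or co-investigator will access the number generator in the pre-op area".
- **Block.** Treatment technique places the Pec block before surgery; afterwards "the patient will be monitored in the preoperative area until he/she is brought into the operating room for their procedure". Control patients are infiltrated in the operating room just before incision.
- **Inclusion.** The two inclusion items, age and partial mastectomy, stand under the heading "Inclusion criteria assessed during surgery".
- **Exclusion.** One bullet reads "Patients who remain intubated overnight after surgery or who are unable to provide information regarding their pain immediately postoperatively". Others carry no time point, for example "Lack of patient cooperation including those patients who refuse a MAC anesthetic" and, under contraindications to regional anesthesia, "Inability to guarantee sterile equipment or sterile conditions for the block".
- **Documentation.** Entry Criteria says only "Subjects will be evaluated and confirmation of the following will be documented". It gives no time and no link to the draw.
- **Consequence.** Enrollment procedures states that patients eliminated for any reason have their records shredded and are left out of the final analysis.

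**The concern.** Randomization makes the arms comparable at the moment of the draw. A criterion applied afterwards keeps them comparable only if treatment cannot influence who meets it. Here it plausibly can. A patient may be unable to report pain soon after surgery because of conversion to general anesthetic, which is a hypothesized treatment effect. Intraoperative opioid could have the same result, and opioid use is the primary outcome. A block complication is a third route: Risks lists lung perforation and intravascular injection, and the toxicity definition under Stopping Criteria includes seizures.

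Removing such patients selects on something close to the outcome. If the Pec arm loses its heavier users, the block looks better than it is; if the control arm does, it looks worse. Because the records are destroyed, the full randomized set could not be rebuilt to see which had happened.

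**Working it through.** **1. Order of events.** Consent; random draw in the pre-op area; Pec block (Pec arm) in the pre-op area; operating room, with infiltration before incision (control arm); surgery; recovery. The quoted exclusion becomes observable only at the last step.

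**2. Which criteria are affected.**

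| Criterion | When it is knowable | Route to bias |
|---|---|---|
| Overnight intubation, or unable to report pain after surgery | Only after surgery | Yes, explicit in the text |
| Sterile conditions for the block, injection-site infection, refusal | Time not stated | Only if applied after the draw |
| Non-cooperation or MAC refusal | Time not stated | Only if applied after the draw |
| Age, partial mastectomy | Baseline or planned, despite the heading | None shown |
| Anticoagulation, pregnancy, language, consent capacity, allergy, liver disease, chronic opioid use | Baseline | None |

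**3. Spread implied by the sample size.** Statistical Considerations gives 56 per group, 80% power, alpha 0.05 and a 35% reduction, but no SD or control mean. I assume a two-sided test and equal SDs, and solve backwards:

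- d = (1.960 + 0.842) × √(2/56) = 0.529
- SD / control mean = 0.35 / 0.529 = 0.66

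The t-test version gives d = 0.534 and a ratio of 0.655. Ratios of 0.60, 0.66 and 0.70 give totals of 94, 112 and 126. The planned 112 is therefore attainable but cannot be verified; 0.66 is used only to scale the illustration.

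**4. Effect of losing k patients from one arm, with no true difference.** If the k removed patients average r times the arm mean, the arm mean falls by

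(k × (r − 1)) / (56 − k).

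With lognormal totals and a coefficient of variation of 0.655, simulation gives:

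| Removed from one arm | Random draw from upper half of users (r ≈ 1.445) | The very highest users |
|---|---|---|
| 1 | 0.445/55 = 0.8% | 4.4% |
| 2 | 0.890/54 = 1.6% | 7.6% |
| 3 | 1.335/53 = 2.5% | 10.2% |

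Against the 35% target, three removals amount to 2.5/35 = 7% of the effect in the first column and 10.2/35 = 29% in the second.

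**5. Power.** Removing 5% of one arm (about three patients) lowers power only from 80% to 79.0%. Bias, not lost precision, is the issue.

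**The case against.** The strongest reply is that this is one bullet in a list that is otherwise almost entirely baseline, and that it will rarely apply. Conversion is to a laryngeal mask airway, so overnight intubation is probably uncommon. Much of this stands. It limits the likely size, but inability to report pain remains the likelier route, and the bullet is worded as something that happens after surgery.

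A second reply is that Enrollment procedures already eliminates anyone who misses questions at the set times, so a patient who cannot give an early pain score would go anyway. The overlap is real. It means that correcting only the Exclusion criteria would not protect these patients; it does not make the exclusion harmless.

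A reader might infer something stronger: that several criteria operate after allocation, and that the block-specific ones remove patients from the Pec arm alone. The documents do not support this. Entry Criteria applies the list to all subjects without reference to arm, and consent precedes the draw, so refusal of the block can be settled beforehand. Nothing says these items are checked only in patients about to be blocked. What can be said is that their timing is unstated, and that they would act unequally if applied after the draw. Likewise, the inclusion heading contradicts allocation before surgery, but no route to bias through age or planned procedure is shown.

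**Conclusion.** The point holds for one exclusion criterion, on explicit text: followed as written, the plan selects patients on a post-randomization event that treatment may influence, then discards the data needed to detect the result. A second, lesser point also holds: no section requires eligibility to be confirmed before the draw.

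The documents give no rate for the event and no direction, so the bias cannot be estimated. For one to three patients lost from one arm, about 1–3% of that arm's mean is a moderate illustration. About 4–10% is the extreme case, because it requires the lost patients to be exactly the highest users, all in one arm; the documents do not link inability to report pain to the highest use. Both ranges assume lognormal totals, a coefficient of variation of about 0.66 and no true effect. It should be corrected before the analysis because it touches the primary comparison and the loss of records is irreversible.

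**What to change.** 1. **Exclusion criteria:** delete the bullet on overnight intubation and inability to report pain. Record the event as an outcome, by arm.
2. **Inclusion heading and Entry Criteria:** retitle and reword so that every criterion, including all contraindications to regional anesthesia, is confirmed and documented for every patient before the random.org draw, on the basis of the planned procedure.
3. **Reasons found after the draw:** treat them as protocol deviations, not ineligibility.
4. **Enrollment procedures:** amend so that these patients stay in the study, their records are retained, and they are analyzed in the assigned arm. Without this step, the first change would have little effect.

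The cost is protocol wording and a one-page pre-draw checklist. A few patients will enter the analysis without an early pain score or without the block. In-facility opioid use is charted, but use after discharge still depends on the planned 24, 48 and 72 hour contacts, so some missing data may remain to be handled.

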### **Assessments:**

Post-operatively patients will be evaluated 1 and 2 hr post-operatively by the PACU nurse and 6 hrs post-operatively by a medical student or research coordinator. This person will not be aware of the patient's mode of analgesia. The medical student or research coordinator will evaluate at, 24, 48, and 72 hours post injection +/- 5 hours. If sent home they will be contacted via preferred contact method at, 24, 48, and 72 hours post-operatively. Patients will be asked to rate their pain on scale of 0-10. The amount of opioids used by the patient will be recorded as will any other adjuvant pain medication used. Any modality related complications will be recorded. The patients will be asked at 72 hours post-injection to fill out a quality of recovery and OBAS survey. All complications will be recorded from time of consent to last follow up date. Patients will be called at 3, 6, and 12 months post operatively to fill out a chronic pain survey.

All data will be recorded in a locked encrypted database. Data collection will continue until Postoperative day ( POD ) #3. Should patients be re-admitted to the hospital in the next two weeks (Up to POD #19) for pain a notation will be made in study records. Additional contacts by the research assistant or medical student will continue up until the 3, 6, and 12 month postoperative times.

An analysis of the total cost of analgesics (including patient costs for opioid prescriptions) will be tabulated at the conclusion of the study to determine the most cost effective treatment option as this will be added into the cost of hospitalization including the number of days each patient spent in the hospital.

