**Benefits:**

There are no benefits to you from your taking part in this research. We cannot promise any benefits to others from your taking part in this research. However, possible benefits to others include pain relief and possibly shorter hospital stay with decreased risk of complications. The only alternative post-operative pain treatment options include intravenous or oral opioids. During the study period, any subject who prefers not to be involved in this study will be treated appropriately as determined by the surgeon and anesthesiologist. There will be no alteration in the post-operative program for those that decline enrollment in this study.

No parties will receive any specific direct benefits from this study with the exception of the patient. The physician and medical community at large may indirectly benefit from learning more about the post-operative pain options for these patients.

**Precautions and corrective actions:** All treatment arms will have the same post-operative protocol. All complications will be noted by the operating physician and reported to the IRB and research staff. Appropriate records will be made in the patient chart and the patient will be treated as needed by the operating physician.

**Project Medications:** All medications will be provided by the hospital pharmacy, and will be noted in the medicine administration record in the chart. No experimental medications will be evaluated in this study.

**Specimens to be collected:** None

**Data collection:** The surgeon, anesthesiology staff, and research staff will collect data. The data will be comprised of outpatient notes, inpatient records, operative reports, intra-operative photos and assessments, questionnaires, study follow-up evaluations. In addition to the surveys used to measure subjective and objective outcome, other data will be collected during patient interviews including:

- Demographic data
- Age
- Weight
- ASA class
- Type and duration of surgery
- VAS Score at 1, and 6, 24, , 48, , and 72 hours after surgery
- Length of stay in recovery room
- Amount of opioids given preop,intraoperatively and post-operatively
- Rate of conversion to general anesthetic
- Satisfaction with treatment
- Quality of recovery survey on 72 hours post-injection
- OBAS at 72 hours
- Chronic pain (pain disability index) at 3, 6, 12 months
- At 72 hours the following will be recorded:
  - Any persistent need for analgesics
  - Total length of stay
  - Total Use of opioids per day

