  - Amount of opioids left over after 3 days
  - Presence of nausea/vomiting in 3 days post operatively
  - Occurrence of any subsequent re-admission over the ensuing 1 month and any complications

The collected data will be compared between groups on a regular basis in order to evaluate the safety and efficacy of the study. All data will be stored in secure locations in the Research Office. Research coordinators working with physicians to collect data at appropriate intervals will ensure complete follow-up. Research coordinators will periodically check physician schedules to ensure that patients being seen for follow-up complete all required questionnaires. Monthly meetings will also be conducted to ensure all patients needing to be evaluated are seen at the appropriate time intervals and that all data is being entered into the appropriate database.

**Data Safety Monitoring:** Authorized study staff and investigators who have gone through HIPAA, CITI, and other data security training through the University of Minnesota will be collecting, managing, and analyzing data. All serious adverse events will be brought forward to the Anesthesia Data Safety Monitoring Board that is comprised of various senior staff anesthesiologists. A formal determination concerning the severity of the risk and the recommended actions required will be submitted in writing to the principle investigator. This report will be submitted to the Institutional Review Board along with the required UPIRTSO documents.

**Statistical Considerations:** The primary outcome measurement used in this study is total opioid use

A sample size of 112 (56 per group) will be enrolled in order to power our study at 80% to detect a 35% decrease in total post-operative opioid usage for our treatment group versus the control with an  $\alpha=0.05$ . This sample size was estimated based on previous estimates for postoperative analgesic consumption from similar trials reported in the Tam (2015) meta-analysis paper.

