### **Outcome Measurements:**

Outcome measures include both clinical assessments and subjective outcome measures reported by the subject on different rating scales.

Distribution of the scores and the clinical evaluations will be examined and cut-points may be assigned to create categorical data. Statistical analysis of parametric data will be done using ANOVA techniques with corrections for repeated measures (when necessary); non-parametric data will be analyzed with Chi-squared techniques. Statistical significance will be defined as  $p < 0.05$ . Power is expected to be 0.8. Data stratification will be done where appropriate. Stratification variables include: pre-operative pain modality.

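### Patients with short-term or intermittent home opioid use can enter, but that use is neither listed for collection nor adjusted for, which costs the primary opioid comparison some precision

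*Combined protocol and SAP*

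**What the plan says.** All references are to the combined protocol and SAP.

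- **Exclusion criteria.** The opioid criterion is "Daily use of opioid for more than three weeks". No dose or look-back period is given. Daily use of three weeks or less, and intermittent use, are not excluded.
- **Statistical Considerations.** "The primary outcome measurement used in this study is total opioid use". The trial enrols 112 patients (56 per group) for 80% power at α = 0.05 "to detect a 35% decrease in total post-operative opioid usage for our treatment group versus the control". The basis is described as follows: "This sample size was estimated based on previous estimates for postoperative analgesic consumption from similar trials". No mean, SD or sidedness is given.
- **Assessments.** "The amount of opioids used by the patient will be recorded as will any other adjuvant pain medication used". Continuing home use is not separated from new use after surgery.
- **Data collection.** The nearest item is "Amount of opioids given preop,intraoperatively and post-operatively". Home use before surgery is not listed.
- **Outcome Measurements.** The methods are ANOVA, corrected for repeated measures where needed, and chi-squared techniques. No covariate is named. The one stratification variable, preoperative pain modality, is undefined.
- **Randomization procedure.** Allocation is by a random number generator, with no stratification by opioid history.

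**The concern.** A patient who was already taking opioids at home may go on taking them after surgery for reasons unrelated to the block. As the outcome is defined, that amount counts in full. A few such patients widen the spread of the primary outcome in both arms, and a few more in one arm than the other would move the estimate. The plan aims at 80% power with no stated margin.

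Baseline opioid use is the pre-surgery counterpart of the outcome, which makes it a natural covariate. If it is not recorded before randomisation, it may be hard to recover reliably later. If it is added to the model after the data are seen, the choice is open to question.

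**Working it through.** **1. The plan's own figure.** The figure of 112 cannot be reproduced, because no mean or SD is given. It can be solved backwards, assuming a two-sided test and taking the control mean as 1 unit:

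- standardised difference = (1.960 + 0.842) × √(2/56) = 0.529
- implied SD = 0.35 / 0.529 = 0.66 of the control mean

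With SD 0.66 and 56 per group, power is 80.1% by the normal approximation and 79.4% by the t-test. The t-test is used below.

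**2. If 0.66 is the SD among non-users.** Let f be the share of prior users and m their extra use in units of the non-user control mean; both are assumed. The effect is held at 0.35, meaning that the block does not reduce the continuing home use.

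- unadjusted variance = 0.66² + f(1 − f)m²
- adjusted SD = 0.66, if the covariate captures the whole difference between users and non-users (the ideal case)

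| f | Use relative to non-users | Added variance | Unadjusted SD | Power unadjusted | Power adjusted |
|---|---|---|---|---|---|
| 2% | 2-fold (m = 1) | 0.0196 | 0.675 | 77.7% | 79.4% |
| 5% | 2-fold (m = 1) | 0.0475 | 0.695 | 75.2% | 79.4% |
| 5% | 3-fold (m = 2) | 0.19 | 0.791 | 64.1% | 79.4% |

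**3. If 0.66 is already the SD of the whole population.** Unadjusted power is then 79.4% by construction. The explained share is R² = f(1 − f)m² / 0.66², and the residual SD is 0.66 × √(1 − R²). For 2-fold use:

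- f = 2%: R² = 0.0196 / 0.4356 = 0.045, SD 0.645, power 81.2% (gain 1.8 points)
- f = 5%: R² = 0.0475 / 0.4356 = 0.109, SD 0.623, power 83.8% (gain 4.4 points)

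**4. Chance imbalance.** At 5% there would be about 6 prior users (0.05 × 112 = 5.6). With 56 per arm, the hypergeometric probability of a 5–1 or 6–0 split in either direction is 2 × (0.0894 + 0.0136) = 0.21. With 2-fold use, a 5–1 split shifts the arm difference by (5 − 1) × 1 / 56 = 0.071 units, or 0.071 / 0.35 = 20% of the target effect. The unadjusted variance in step 2 already contains this, so it is the same loss seen another way.

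**The case against.** The case for leaving the plan alone has several parts.

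- **The size is not established.** This stands. The documents give neither the share of prior users nor their excess use, and whether 0.66 belongs to non-users or to everyone is a modelling choice. If prior users' consumption also fell by 35%, the shortfall would largely vanish. At 5% and 2-fold use the effect becomes 0.35 × 1.05 = 0.3675, the average variance is 0.66² + 0.0475 × (1 + 0.65²)/2 = 0.469, and unadjusted power is about 80%.
- **Nearby text may cover it.** This stands only in part. Opioids given before surgery are listed beside intraoperative and postoperative amounts, which reads as perioperative administration. The undefined stratification variable most naturally means analgesic technique, since the protocol speaks elsewhere of complications related to the modality. Outpatient notes are a data source, so some history may be retrievable, but no amount is specified for collection or analysis.
- **Other prognostic variables could be named as well**, such as axillary dissection, which changes the anesthetic. That is fair, but it does not remove the case for the baseline version of the outcome.

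A reader might also infer a large gain from adjustment. With 5% of patients at 3-fold use, one can obtain 72% unadjusted against 86% adjusted, and with 10%, 69% against 92%. Those adjusted figures arise because the effect is set at 35% of a mean that prior users have raised (0.385 and 0.42 units instead of 0.35). If the excess is continuing home use, the effect stays at 0.35 and adjusted power is about 79%. Nothing in the documents supports 3-fold use.

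**Conclusion.** The gap is real and minor. Eligible patients may bring home opioid use into the primary total, and the plan neither lists that use for collection nor adjusts for it.

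On 2–5% prior users at twice the typical use, power is about 75–78% unadjusted against about 79% adjusted if 0.66 is the non-user SD. If 0.66 covers everyone, there is no shortfall and adjustment adds about 2–4 points. These figures rest on a two-sided test, an effect fixed at 35% of the non-user mean, an SD solved backwards from the sample size, and an assumed share and excess. With 3-fold use the loss would be larger (64% unadjusted at 5%), but that case is hypothetical.

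The documents do not support reading this as bias or as a demonstrated lack of power. Random allocation protects the comparison from systematic error.

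**What to change.** 1. Before randomisation, record one new field: any home opioid use within a defined look-back period, with the usual daily amount.
2. Pre-specify it as a single covariate in the primary opioid analysis, choosing in advance between any use (yes/no) and daily amount. A covariate with several categories is impractical, because 2–5% of 112 is about 2 to 6 patients.
3. Add a sensitivity analysis that excludes prior users.
4. State whether continuing home opioid use counts in the primary total, and define the preoperative pain modality named as a stratification variable.

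The eligibility rule need not change. The cost is one short question and one degree of freedom. It is not quite free: the exclusion check needs only a yes/no answer on daily use beyond three weeks, so intermittent use, shorter daily use and usual amount are new information.
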